PROTOCOL

TITLE. Rituximab (RTX) Therapy in Patients With Active TAO

NCT 02378298

Date 2011-08-24

Background

Every year, 2000 patients in Sweden get the diagnosis of a diffuse autoimmune hyperthyroidism (Grave's disease (GD)). About 40% of the patients with GD have some complaints from their eyes indicating thyroid associated ophthalmopathy (TAO) in its mild form. Moderate-severe forms are seen in approximately 5-10% of GD patients. TAO is an autoimmune complication of GD and the inflammation causes swelling of the periorbital fat, muscles and connective tissue. The patient obtains symptoms such as red eyes, pain, epiphora, diplopia and sometimes exophthalmos. This affects the patient's quality of life (QoL) negatively.

Today, the primary treatment of moderate-severe TAO is high doses of intravenous (iv) steroids, with the purpose to suppress the inflammation. High doses of iv steroids cause side effects, therefore, it is motivated only in moderate-severe cases. Even when the treatment is given early in the course of the disease, only 70-80% of the patients respond to the treatment (responders). The treatment effect on the inflammation is most commonly measured with Clinical Activity Score (CAS) – a score recommended by the European Group of Graves orbitopathy (EUGOGO).

Ten years ago, small observational studies reported promising result on Rituximab (RTX) treatment in TAO, given less side-effects. RTX is an immunomodulating drug where antibodies affect B-cells.

Objectives

The primary aim of this study is to evaluate the effect of Rituximab (RTX) in Thyroid Associated Ophthalmopathy (TAO) patients who are non-responsive to treatment with iv GC (NR-RTX), with patients controls that continued with iv GC even though they did not respond (NR-C). A second aim is to compare the NR-RTX patients with the steroid responsive ones (R-GC) and NR-C, regarding background variables (gender, age, smoking status, duration of GD, duration of eye symptoms, thyroid treatment and lab) and efficacy variables (CAS, CAS SU/M, severity, proptosis and subjective diplopia). Lastly, a third aim is to evaluate and compare the QoL between the R-GC and the NR-RTX in the study at given time points.

Research questions

Does RTX lower the CAS of the non-steroid responsive TAO-patients (NR-RTX), in comparison to NR-C, that continued with iv GC, and R-GC? Do the background variables differ between NR-RTX and NR-GC or R-GC? And lastly, does the QoL differ between the R-GC and the NR-RTX at given measuring points?

Material and Methods

Study design

The RTX-study is a non-randomized prospective study that covers patients with moderate-severe TAO with indication for treatment with iv GC. For this study, a control group (NR-C) will be created.

Patients with TAO are evaluated at Department of Ophthalmology at Sahlgrenska University Hospital/ Mölndal's and are asked for participation if eligible. Variables collected at each visit Clinical Activity Score (CAS), Quality of Life (QoL) through ThyPRO self-assessment questionnaire, biochemical tests (fT4, fT3, TSH, TRAb, liver function tests, fasting blood glucose), blood pressure and waist. An oral glucose tolerance test (OGTT) is performed at 12, 18, and 46 weeks, and a short adrenocorticotrophic hormone (ACTH) test at 12 and 46 weeks. Dual-energy x-ray absorptiometry (DXA) of the spine is conducted at 0 and 18 weeks.

All patients in the RTX-study start the 12-week scheme of iv GC at baseline. After four weeks of treatment, an evaluation of the treatment outcome is made. If the patients have improved their CAS score by ≥ 2 points, they are classified as responders to iv GC (R-GC) and continue their 12-week iv GC scheme. The remainder of the patients are classified as non-responders to the treatment with iv GC and are switched to 1000 mg iv RTX in week 5 and 7, combined with a weekly oral dose of 12.5 – 15 mg MTX (NR-RTX). The RTX is administered at the department of Rheumatology at Sahlgrenska University Hospital. All included patients have thereafter follow-up visits at week 12, 18, 32, 46 and 68 weeks after baseline.

At week 18 and at all follow-up timepoints thereafter, patients in R-GC group are evaluated for possible relapse. If a patient in R-GC has a CAS ≥ 4 points and CAS has worsened by ≥ 2 points compared to the value measured in the prior evaluation time-point, the patient is

considered having a relapse. Patients with relapse are randomized to either treatment with RTX and MTX or with *per oral* GC and MTX.

All patients included in the study are assessed according to study protocol, but if DON is developed, the affected patient is treated outside the study protocol in order to follow DON treatment regimen. The patients with DON still have the same evaluation time points as the other patients in the study, but they are excluded from the comparisons between groups after the occurrence of DON.

From the group of patients with moderate – severe TAO with indication for treatment with iv GC that do not meet inclusion/exclusion criteria for the RTX-study or declined participation, a control group (NR-C) of non-responders will be created. As they are not included in the RTX study, they continue with their 12 weeks scheme of iv GC treatment.

Data collected at the follow-up timepoints: QoL, safety data and information on adverse events.

Study population

Inclusion criteria for the RTX study: man or woman between 18-70 years old, TAO with 7-point score system of CAS ≥ 4 (less than 3 months old), euthyroid for at least 6 weeks.

Exclusion criteria for the RTX study were: DON, ulcerative corneal involvement, previous treatment with steroids for TAO (except for prophylaxis for TAO in connection with RAI), previous treatment with RTX, positive Hepatitis B or C serology, obtained a living vaccine within 4 weeks prior RTX+MTX to evaluation, history of recurrent significant infection or history of recurrent bacterial infections, assessment by the investigator that the patient may not attend to the protocol, current pregnancy or lactation, significant cardiac disease, including significant or uncontrolled arrhythmia, previous active tuberculosis, bone marrow depression with leukopenia, thrombocytopenia or significant anaemia, allergy to the active substance or any other substance in the medications or murine proteins, active, severe infections (such as tuberculosis, sepsis or opportunistic infections), patients with severe immunosuppression, severe cardiac failure or severe uncontrolled heart disease.

The TAO patients not included in the RTX-study will be identified using the diagnosis-related group (DRG) registry according to the 10th revision (ICD-10) in VGR. In DRG, a combination of different codes was used (TAO [H06.2], Graves' disease [E05.0] and iv infusion [DT016]).

Efficacy variables

In the study, both patients' eyes are evaluated regarding CAS and the score of and any improvement of the worst eye was used.

The proptosis is measured in both eyes using the Hertel exophthalmometer.

The ThyPRO questionnaire is a thyroid specific QoL self-assessment questionnaire. It is one questionnaire that measures QoL within 13 different dimensions: goitre symptoms, hyperthyroid symptoms (constitutes two dimensions), eye symptoms, tiredness, cognitive function, anxiety, depressivity, emotional susceptibility, impairment of social, daily and sex life and lastly cosmetic complaints. ThyPRO consists of totally 84 questions. The scores for each dimension can be presented as raw or normalised score (raw score/max score x 100) that ranges from 0 to 100. A high normalised score indicates decreasing QoL (i.e. more symptoms or greater impact of disease).

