1 STUDY DETAILS

1.1 Study Objectives

- A. Do the background variables differ between NR-RTX and R-GC or NR-GC?
- B. Does RTX lower the CAS of the non-steroid responsive TAO-patients (NR-RTX), in comparison to NR-C, that continued with iv GC, and R-GC?

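### The aim asks about rituximab alone, but every NR-RTX patient also receives methotrexate, so the comparison with NR-C cannot isolate an effect of RTX from MTX

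*Protocol*

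**What the plan says.** The Protocol (Objectives) sets the question as a single-drug one: "The primary aim of this study is to evaluate the effect of Rituximab (RTX) in Thyroid Associated Ophthalmopathy (TAO) patients", to be compared "with patients controls that continued with iv GC even though they did not respond (NR-C"). The Protocol's Research questions ask "Does RTX lower the CAS of the non-steroid responsive TAO-patients (NR-RTX), in comparison to NR-C, that continued with iv GC, and R-GC"; SAP section 1.1, objective B, repeats this. MTX appears in none of these statements.

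The treatment is described in the Protocol under Material and Methods, Study design. Patients whose CAS has not improved by at least 2 points after four weeks are moved to RTX, given at weeks 5 and 7, "combined with a weekly oral dose of 12.5 – 15 mg MTX (NR-RTX"). For the controls, the same section says "As they are not included in the RTX study, they continue with their 12 weeks scheme of iv GC treatment". It says nothing about MTX for them, either way.

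SAP section 3 specifies Mann-Whitney, Fisher and Mantel-Haenszel tests of NR-RTX against each other group in turn. The variable lists in SAP section 2 contain no MTX exposure item, and MTX is not mentioned in SAP sections 1 to 3.

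**The concern.** The group called NR-RTX receives two added drugs, and the objective names one of them. Within that group RTX and MTX always go together. If NR-RTX has lower CAS than NR-C, the plan's own question would be answered yes for RTX, although the same data would look identical if MTX had produced part of the difference.

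What is at stake is what the trial may conclude, not how any test is computed. The adverse-event comparison of NR-RTX with R-GC (SAP section 2.3.2) carries the same single-drug label, so harms could be credited to the wrong drug as well. The Protocol gives RTX at weeks 5 and 7, does not state how long MTX continues, and follows patients to week 68, which is 68 − 7 = 61 weeks after the second infusion. Late differences are thus particularly hard to assign to one drug.

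**Working it through.** The plan states no sample size, power or effect size (SAP section 1.4 says that no power calculation was done), so there is no figure to reproduce. The question is which treatment effects the contrast can identify.

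**Inputs (Protocol, Study design), after the week-4 evaluation**

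| Group | RTX | MTX | iv GC continued |
|---|---|---|---|
| NR-RTX | yes, all | yes, all | no (inferred from the patients being switched) |
| NR-C | no (outside the RTX-study) | not mentioned; taken as no | yes, to 12 weeks |

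**Step 1. Model.** For illustration, let mean CAS change = intercept + RTX + MTX + GC, additive, with columns in that order. NR-RTX has row (1, 1, 1, 0) and NR-C has row (1, 0, 0, 1). The matrix has rank 2 for 4 parameters.

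**Step 2. What is identified.** Subtracting the rows gives (0, 1, 1, −1), so the observed difference is D = RTX + MTX − GC. RTX alone, (0, 1, 0, 0), is not a combination of the two rows and is not identified.

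**Step 3. Allow for the stated comparator.** Since the aim compares RTX with continued iv GC, the target could fairly be read as RTX − GC, that is (0, 1, 0, −1). Writing this as a × (NR-RTX row) + b × (NR-C row), the RTX column needs a = 1 and the MTX column needs a = 0. These contradict each other, so RTX − GC is not identified either. If both groups had MTX, the rows would be (1, 1, 1, 0) and (1, 0, 1, 1), the difference would be (0, 1, 0, −1), and RTX − GC would be identified. MTX alone is the obstacle.

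**Step 4. Illustration with assumed values; none is in the documents.** Take D = −2 CAS points. Then RTX − GC = D − MTX:

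- MTX 0: −2 − 0 = −2
- MTX −1: −2 + 1 = −1
- MTX −2: −2 + 2 = 0

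One observed difference fits both a full and a null contribution from RTX relative to iv GC. These values show non-identification. They are not an estimate of the share due to MTX.

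**Step 5. Other comparisons in the plan.** R-GC does not fill the gap: it is selected on response and is described as receiving iv GC only, until relapse. The relapse randomisation gives MTX in both arms (RTX and MTX, or oral GC and MTX), but it concerns relapsing responders, a different population from the primary contrast.

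**Step 6. If some NR-C patients took MTX.** With a fraction p of NR-C on MTX, D = RTX + (1 − p) × MTX − GC. MTX drops out only at p = 1. Recording p is therefore informative, but the plan as written does not collect it.

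**The case against.** The strongest reply is that nothing is concealed. The Protocol introduces the NR-RTX label in the same sentence that describes RTX combined with MTX, one exclusion criterion refers to the pair, and the relapse arm names both drugs. On that view NR-RTX is shorthand for a defined regimen, and the remedy changes no endpoint, test, population or sample size. It is true that the regimen is disclosed and that the change is wording. But disclosure in the methods does not correct an aim and a SAP objective that ask a different question.

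A reader might infer several stronger things, and the objection is right that the documents do not support them:

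- *That stopping iv GC is a further flaw.* The aim names controls who continued iv GC, so switch versus continue is the stated comparison.
- *That MTX use in NR-C is zero by design.* The Protocol describes only iv GC for these patients and neither forbids nor records MTX. Zero is a reasonable inference, not a stated fact.
- *That the study can show nothing about RTX.* It cannot isolate RTX; it can still describe RTX plus MTX beside continued iv GC.
- *That a planned conclusion is wrong.* Neither document contains a planned conclusion or interpretation rule. What is wrong as written is the question.
- *That MTX explains some stated share of the effect.* No figure in the documents bounds it, and a limit of 0% to 100% would itself assume that the drugs do not act in opposite directions.
- *That renaming the regimen gives a causal effect of switching.* NR-C is drawn from patients who were ineligible or declined, allocation is not randomised, and the tests are unadjusted.

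**Conclusion.** The point holds as one of attribution. The primary aim, the research question and SAP objective B ask about RTX, while the NR-RTX versus NR-C contrast carries RTX and MTX together and cannot isolate one from the other. More patients or baseline adjustment would not change this, because no NR-RTX patient is planned to receive RTX without MTX.

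Its size cannot be given in CAS points: the portion of any difference belonging to MTX is unknown. The finding rests on two readings of the Protocol. MTX is documented for all of NR-RTX, and its absence in NR-C is inferred from silence. The additive model in the working is only a device; without additivity, RTX and MTX would be no easier to separate. Selection of NR-C is a separate source of bias that rewording does not cure. The change should be made, because it alters what the trial may claim.

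**What to change.** 1. Reword the primary aim (Protocol, Objectives), the research question (Protocol, Research questions) and objective B (SAP section 1.1) along these lines: *to compare CAS in GC non-responders switched to RTX plus MTX with CAS in non-responders who continued iv GC, as a non-randomised comparison.* Keep R-GC as the additional comparison.
2. Add to SAP section 3 a statement that no difference in CAS or adverse events, from NR-RTX versus NR-C or NR-RTX versus R-GC, will be attributed to RTX alone.
3. Label the group RTX+MTX in SAP section 1.3 and in all tables.
4. Record concomitant MTX use in NR-C where the charts hold it, and report it; otherwise state that it is unknown.

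The first three items cost only wording, and the fourth a chart check. The downside is a less favourable claim, covering a regimen rather than a single drug. No treatment change is proposed.

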2.3 Analysis Variables

2.3.1 Primary Variable

- Change of CAS (clinical activity score) between the observation timepoints and the previous timepoint: comparison between the treatment groups
- CAS: comparison between the treatment groups at the different timepoints

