3 STATISTICAL METHODOLOGY

Tests between groups will be made for the NR-RTX group and all of the other groups one at a time; R-GC and NR-C (where applicable).

For continuous variables Mann-Whitney U-test will be used for analyses between two groups. For dichotomous variables Fisher exact test will be used for test between two groups. For ordered categorical variables Mantel Haenszel Chi Square test will be used for test between two groups.

For all continuous variables Wilcoxon's Signed-Rank test will be used for within group analyses.

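### Steroid responders who relapse are re-treated, half of the randomised options being RTX, yet their later CAS stays in the NR-RTX v R-GC comparison with no sensitivity analysis

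*Protocol*

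**What the plan says.** **Relapse and rescue (Protocol, Study design).** "At week 18 and at all follow-up timepoints thereafter, patients in R-GC group are evaluated for possible relapse". The rule has two parts. The level part asks for a score of 4 or more. The change part reads: "CAS has worsened by ≥ 2 points compared to the value measured in the prior evaluation time-point". On what happens next, the protocol says: "Patients with relapse are randomized to either treatment with RTX and MTX". The alternative arm is oral GC with MTX. Follow-up visits are at weeks 12, 18, 32, 46 and 68.

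**Events that end a patient's contribution (Protocol, Study design).** Only optic neuropathy (DON) has such a rule. These patients keep their visits, but "they are excluded from the comparisons between groups after the occurrence of DON". No sentence does the same, or the opposite, for relapse.

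**Analysis (SAP).** Section 2.3.1 lists two primary variables. One is a visit-to-visit change: "Change of CAS (clinical activity score) between the observation timepoints and the previous timepoint: comparison between the treatment groups". The other is a level at each visit: "CAS: comparison between the treatment groups at the different timepoints". Section 2.3.2 adds change from baseline. Section 3 tests NR-RTX against R-GC and against NR-C, one at a time: "For continuous variables Mann-Whitney U-test will be used for analyses between two groups". The SAP text does not mention relapse, re-treatment or a sensitivity analysis. That CAS after rescue stays in the comparison is therefore inferred from silence; the SAP does not state it.

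**The concern.** Objective B (SAP 1.1) asks, among other things, whether RTX lowers CAS in comparison with R-GC. Once a responder has relapsed and been re-treated, later CAS no longer describes a response to the iv GC course. It describes iv GC followed by rescue, and for some patients the rescue is the drug under study. In the change-from-previous variable, the fall after rescue is credited to R-GC as improvement. A reader of the late results could not tell how much of an apparent R-GC advantage, or of a missing RTX advantage, comes from rescue. The DON rule shows that the authors saw this kind of problem for one event.

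**Working it through.** The documents give no relapse rate, CAS variability or sample size (SAP 1.4: no power calculation), so there is no planned figure to reproduce. All sizes below rest on assumed inputs.

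**1. Which visits can be affected.** The first relapse assessment is at week 18, so rescue can change CAS from week 32. A relapse first found at week 68 cannot change the week-68 value.

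**2. Shift in the R-GC mean.** Shift = −(share flaring) × (share caught) × (fall after rescue).
- With 10–30% flaring, 50–100% caught and a fall of 2 points: from −0.1 × 0.5 × 2 = −0.1 to −0.3 × 1 × 2 = −0.6.
- Main scenario: 20% flare to CAS 5, rescue returns them to 2, other R-GC patients stay at 2. All caught: −0.2 × 3 = −0.6, so the mean is 2.0 instead of 2.6. If rescue reaches only CAS 3: −0.2 × 2 = −0.4.

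**3. Mann-Whitney scale at week 46, without measurement noise.** This is P(R-GC CAS > NR-RTX CAS) + ½ P(tie), where 0.5 means no difference. NR-RTX is assumed 80% at CAS 2 and 20% at CAS 4.
- An R-GC patient at CAS 2 contributes 0.8 × 0.5 = 0.40; one at CAS 5 contributes 1.
- Planned, all flares caught: 0.40.
- CAS at relapse carried forward: 0.8 × 0.40 + 0.2 × 1 = 0.52.
- If NR-RTX were all at CAS 2 instead: planned 0.50, carried 0.8 × 0.5 + 0.2 × 1 = 0.60.

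**4. The same with visit noise (SD 0.6; 200,000 simulated paths per flare shape, CAS rounded and limited to 0–7).** The paths at weeks 4, 12, 18, 32, 46 and 68 are 2, 2, 2, 5, 5, 5 (one-step) and 2, 2, 3, 4, 5, 5 (stepwise). The rule fires in 97% and 68% of them (SD 0.4: 99% and 43%; SD 0.8: 96% and about 80%).

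| 20% flares, SD 0.6 | all one-step | 50:50 | all stepwise |
|---|---|---|---|
| R-GC mean, week 46, planned | 2.03 | 2.18 | 2.33 |
| R-GC mean, week 68, planned | 2.02 | 2.11 | 2.21 |
| Mann-Whitney, week 46, planned | 0.41 | 0.44 | 0.47 |
| Mann-Whitney, week 46, carried | 0.52 | 0.52 | 0.52 |
| Gap, week 46 | 0.11 | 0.08 | 0.05 |
| Mann-Whitney, week 32, planned | 0.52 | 0.50 | 0.48 |
| Mann-Whitney, week 32, carried | 0.52 | 0.51 | 0.50 |

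With 10% flares the week-46 values are 0.41–0.44 planned and 0.47 carried; with 30%, 0.41–0.50 and 0.57–0.58. The small week-32 gap partly reflects the assumed timing, since few of these flares qualify at week 18.

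**5. What drives the gap.** It is largest (0.11) where nearly every flare is caught and smallest (0.05) where about a third are missed. More rescue means more distortion.

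**6. Change from week 32 to 46 in R-GC.** One-step, no noise: 0.2 × (2 − 5) = −0.6; with SD 0.6, −0.57. Stepwise: 0.2 × (5 − 4) = +0.2; with SD 0.6, 0.00. Carrying values forward does not repair this variable, because every change after relapse becomes zero by construction.

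**7. Bias of the carried analysis.** For R-GC patients truly stable at CAS 3–5, noise triggers make the carried mean too high by 0.05, 0.10 and 0.15 at weeks 32, 46 and 68 (SD 0.6). At week 68 this is 0.03 with SD 0.4 and about 0.31 with SD 0.8. If untreated relapses in 20% would have fallen by 1 or 2 points, it is too high by 0.2 × 1 = 0.2 or 0.2 × 2 = 0.4. Both favour RTX. If relapses would have gone on rising, it is slightly low (2.56 v 2.60 at week 46, stepwise).

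**8. Comparing p-values does not help.** In the 50:50 scenario, with assumed group sizes of 10 v 20 or 15 v 30, the two tests fall on the same side of p = 0.05 in about 88–90% of runs (78% at 30 v 70). Yet the true gap is 0.08 and comes wholly from re-treatment.

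**The case against.** Comparing patients as managed, with protocol-specified relapse treatment included, is a legitimate question. That stands, so the planned test should be kept. But the SAP does not say that this is the question, and it gives the reader no means of seeing how much rescue contributes.

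The comparison is also weak for a deeper reason. R-GC is selected by a CAS fall of at least 2 points at week 4 in a non-randomised study, so responders are set against non-responders at every visit. No handling of relapse cures that. This stands too, and it limits the weight of the point.

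Carrying the relapse value is itself biased, mostly towards RTX. This is true and has to be stated with the result; a difference between the two analyses may be partly that bias.

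A reader might instead blame the relapse rule, because a rise of 1 point per visit (2, 3, 4, 5, 6 from week 12 to week 68) never meets it. That reading of the rule is literally correct, but it does not explain the problem: a rule that caught every flare would widen the gap. The documents give no ground here for changing the rule.

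**Conclusion.** The point holds as a gap in the analysis plan for a secondary comparison. CAS after rescue enters the NR-RTX v R-GC results from week 32, and mainly at weeks 46 and 68. Under the assumed inputs with 20% flares, the planned week-46 result leans towards R-GC (0.41 to 0.47) where the carried analysis is near no difference (0.52). The size in this trial cannot be known: the relapse rate, visit noise, response to rescue and NR-RTX distribution are all assumed, and with few relapses the effect is small.

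Two stronger readings are not supported. The first is that the trial's main result is compromised: the primary aim is NR-RTX v NR-C, and the relapse rule applies only to R-GC. The second is that agreement between the planned and sensitivity tests would show that re-treatment does not matter: in a small study they mostly agree because both are non-significant.

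**What to change.** Keep the planned test and add to SAP 2.3.1 and 2.3.2:

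- **CAS level and change from baseline, NR-RTX v R-GC, weeks 32, 46 and 68.** Repeat the analysis with each R-GC CAS recorded after relapse randomisation replaced by the CAS at relapse. Report the effect estimate (for example, the Mann-Whitney probability) with its confidence interval beside the planned estimate. Do not judge dependence on rescue by comparing p-values.
- **Change from the previous timepoint.** In the sensitivity analysis, leave out R-GC intervals that begin at or after re-treatment; keep the interval that ends at the relapse visit. The remaining late intervals describe only patients not yet re-treated, and the report should say so.
- **Counts.** Give the number of R-GC patients re-treated, by visit and by randomised arm.
- **Interpretation.** State that the carried analysis favours RTX, because it allows no later improvement and carries noise triggers forward, and that it is read beside the planned result, not instead of it.

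The cost is one SAP paragraph, one repeated analysis and a count, all from CAS already collected. Visits, treatment and the relapse rule do not change. The downside is an extra result with a known direction of bias.

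### NR-C, the comparator for the primary aim, is selected partly on a CAS threshold, and the CAS comparisons make no adjustment for starting CAS

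*Protocol*

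**What the plan says.** The primary aim (Protocol, Objectives) sets NR-RTX against "with patients controls that continued with iv GC even though they did not respond (NR-C"; SAP 1.1, objective B, repeats the contrast. Under Study design, the controls come from patients with an indication for iv GC "that do not meet inclusion/exclusion criteria for the RTX-study or declined participation, a control group (NR-C) of non-responders will be created". They are found through diagnosis and infusion codes (Study population). No minimum CAS, matching or restriction is stated for them.

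The RTX-study inclusion criteria contain "TAO with 7-point score system of CAS ≥ 4 (less than 3 months old), euthyroid for at least 6 weeks". NR-RTX patients therefore start at CAS 4 or more; nothing requires this of NR-C.

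The response rule is written for patients in the RTX study: "If the patients have improved their CAS score by ≥ 2 points, they are classified as responders to iv GC (R-GC". So is the visit schedule: "All included patients have thereafter follow-up visits at week 12, 18, 32, 46 and 68 weeks after baseline". Of the controls the Protocol says: "As they are not included in the RTX study, they continue with their 12 weeks scheme of iv GC treatment".

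SAP 2.3.1 makes two CAS variables primary: change since the preceding timepoint, and the level at each timepoint. Change from baseline is secondary (2.3.2). SAP 3 compares NR-RTX with each other group in turn, by Mann-Whitney for continuous and Mantel-Haenszel chi-square for ordered categorical variables. No covariate or stratification factor is named. CAS is not in the baseline list of SAP 2.1. SAP 1.4 reports no power calculation, and neither document gives a sample size or SD.

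**The concern.** A control group formed partly from patients who failed a criterion on the outcome scale may start at a different point on that scale. CAS is bounded at 0, and a patient who starts lower has fewer points to lose. If NR-C starts lower, it will tend to show a lower level later (which looks bad for RTX) and a smaller early fall (which looks good for RTX), with no drug effect at all. The two primary variables could then point in opposite directions, and the plan contains no adjusted estimate to settle between them. Change scores do not solve this: subtracting an earlier value is not adjusting for it when the expected fall depends on the starting value.

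**Working it through.** The plan has no power figure to reproduce, so the check is a simulation in which **every numerical input is assumed**.

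**Inputs.** 15 NR-RTX and 20 NR-C; two-sided 0.05. Week-0 CAS 4/5/6/7 with probability 0.40/0.35/0.18/0.07. A share of the NR-C source pool (0, 10 or 25%) instead has CAS 2/3 with probability 0.35/0.65. CAS at a visit = week-0 CAS × (1 − proportional fall) + noise, rounded and limited to 0-7; between-patient SD of the fall 0.20, noise SD 0.7 points. Mean fall at week 4 and the next visit (week 12): 40% and 65%, or 50% and 70%. Only patients with a week-4 fall below 2 points are kept, in both groups. The main runs use 2,000 trials per cell, so the Monte Carlo standard error at a 5% rate is √(0.05 × 0.95 / 2000) = 0.5 percentage points.

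The second fall scenario gives 23% non-response among eligible patients, inside the 20-30% implied by "only 70-80% of the patients respond to the treatment (responders" (Protocol, Background). The first gives 36%, outside it. The Protocol does not tie that response figure to the week-4 rule.

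**Mechanism.** In the first scenario, before selecting non-responders, a gap of g points at week 0 becomes (1 − 0.65) × g = 0.35g in level at week 12, and (0.65 − 0.40) × g = 0.25g in the week 4 to 12 change. For g = 2 these are 0.70 and 0.50 points, in opposite directions for RTX. Selecting on a fall below 2 points enriches low starters: 10% or 25% of the pool becomes 17-22% or 38-46% of NR-C.

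**No RTX effect: false p<0.05 at week 12** (ranges cover both fall scenarios and repeat runs)

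| Share of pool below CAS 4 | 0% | 10% | 25% |
|---|---|---|---|
| Level, Mann-Whitney | about 4% | 8-11% | 20-30% |
| Change from week 4, Mann-Whitney | 4-5% | 5-7% | 10-14% |
| Linear regression on group, week-0 and week-4 CAS | 4-5% | 5-7% | 4-7% |

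At 25%, the mean bias is 0.52-0.62 points towards NR-C for level and 0.26-0.30 towards RTX for change.

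**Later visits.** With further falls assumed and a 25% share, change from the previous timepoint at weeks 18 and 32 rejects in 4-6% (bias about 0.06 points), while level still rejects in 18-27%.

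**True 1-point effect, week 12, share 0/10/25%.** Power on level is 63-67/35-40/12-18%. Power on change is 77-80/86-88/93-95%, but that rise is bias: the mean difference goes from 0.97 to 1.1 to 1.25. Regression holds 80-83/82/79-80%, with a mean estimate of 0.97-0.99.

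**Second model.** Follow-up CAS depends on week-4 CAS only, with 12, 20 or 30 per group and 25% of NR-C itself below CAS 4. The directions are the same: level rejects in 7.5-19%, change in 6-13%, and adjustment for week-4 CAS gives about 4-6%.

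**Where adjustment is not needed or does not help.** If 25% of the pool instead has CAS 6-7, errors stay near nominal (level 6-8%, change 5%, regression 4-5%). If 25% or 50% of NR-C run 1 point worse for an unmeasured reason, every test favours RTX by about 0.25 × 1 = 0.25 or 0.50 × 1 = 0.50 points, and regression on CAS still errs in 10% or 27-28%.

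**The case against.** The strongest reply is that low starting CAS in NR-C is assumed, not documented. The controls must have moderate-severe disease with an indication for iv GC. The CAS threshold is one of about twenty entry criteria, most of them about safety, comorbidity or practicality, and declining is another route in. This stands. A reader might infer that NR-C does start lower, or that the 25% share describes this trial; no passage says that any control has CAS below 4. Size and direction are unknown.

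Three further inferences also go beyond the documents or the figures:

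- *Change is biased at every visit.* The bias is shown only from week 4 to week 12. From week 18 on, the preceding timepoint is no longer week 4, and visit-to-visit change is near nominal in the later visits checked.
- *A week-0 comparison would usually expose the imbalance.* In the simulation it is significant in only 14-20% of trials at a 10% share and 53-70% at 25%. Even when it shows an imbalance, it corrects nothing.
- *NR-C are classed by a different response rule.* The Protocol calls them non-responders and defines the term once, so reading the definition across is natural. This is a clarity gap only.

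It can also be said that the study is openly non-randomised, that background variables are compared between groups, and that unmeasured prognosis may matter at least as much as CAS. All true. But none of this carries starting CAS into the CAS comparison, and regression on CAS does not cure unmeasured confounding.

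**Conclusion.** The point holds as a conditional weakness in the primary contrast. NR-C is selected on criteria that include CAS ≥ 4, or by declining, and CAS is analysed with no adjustment, matching or restriction. If NR-C starts lower, level is biased towards NR-C throughout follow-up and the first change after week 4 is biased towards RTX. The error rates in the table rest on assumed group sizes, CAS distributions and falls: serious for level at a 25% share, modest for level and slight for change at 10%, absent at 0%. The documents do not support a claim that the trial's result is biased, or in which direction. They do support prespecifying an adjusted analysis: it keeps its error rate near 5% in the starting-CAS scenarios examined, and costs no power when there is no imbalance and no missing CAS (80-83%, against 77-80% for change and 63-67% for level).

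**What to change.** 1. For NR-RTX v NR-C, make the primary CAS analysis one linear regression of CAS at one named follow-up visit (for example week 12, the first after the week-4 evaluation) on group, week-0 CAS and week-4 CAS. Apply the same model at later visits as secondary analyses. Keep the Mann-Whitney tests as supportive.
2. State that, for the analysis, the ≥ 2-point week-4 rule also classes NR-C patients, and report how many cannot be classified.
3. Tabulate the reason for non-inclusion of each NR-C patient. Repeat the regression in NR-C patients with week-0 CAS ≥ 4 as a sensitivity analysis.
4. Report the contrast as observational, since CAS adjustment does not remove confounding by unmeasured prognosis.

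**Cost.** SAP wording and record review. No passage says that week-0, week-4 or follow-up CAS exists for NR-C, and controls without the needed values are lost. With loss at random, simulated regression power for a 1-point effect falls from about 80% with 20 controls to 72-77% with 15 and 61-65% with 10. The restricted sensitivity set keeps 20 × (1 − 0.22) to 20 × (1 − 0.17), about 16-17 controls, at a 10% share (power 76-77%), or 20 × (1 − 0.46) to 20 × (1 − 0.38), about 11-12, at 25% (power 67-69%). That is why it should not be the primary analysis.
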